### **5. Study Design**

#### **5.1. Design**

This is a 9-visit randomized, double-blind, placebo controlled, parallel group study evaluating the effectiveness of 4 doses of mepolizumab for the treatment of refractory chronic cough in patients with eosinophilic airways disease (Figure 1). We plan to complete 15 subjects in each arm of the clinical trial. The duration of intervention will be 12 weeks, during which

subjects will receive 4 doses at days 0, 28, 56 and 84. The effects of mepolizumab on objective cough frequency will be tested at week 14, 2 weeks following the last dose of mepolizumab/placebo.

**Figure 1.** Study flow diagram detailing the study visits and procedures per visit per subject following enrolment.

## 5.2. Duration of Study

The total length of a subject's participation in the trial is up to 16 weeks;

- Up to 2 weeks screening period
- 14-week intervention period

## 5.4. Study Period

Estimated date of first subject Q2 2021

Estimated date of last subject Q4 2022

## 5.5. Study Population

Male and female patients  $\geq$  18 years of age assessed in a secondary care clinic for chronic cough due to asthma and/or NAEB.

## **5.6. Inclusion Criteria**

The following inclusion criteria must be met for patients to enter the screening phase of the study:

1. Male sex and female sex patients
2. Aged  $\geq 18$
3. Subjects with a history of chronic cough (cough lasting for  $>8$  weeks)
4. Evidence of airway eosinophilia (sputum eosinophilia  $\geq 2\%$ )
5. FEV1  $\geq 70\%$  of predicted
6. Normal chest x-ray (within the last 2 years)
7. At least one dose of a COVID-19 vaccine a minimum of 2 weeks prior to enrollment

## **5.7. Exclusion Criteria**

Patients should not enter the study if any of the following exclusion criteria are fulfilled:

1. Symptoms of upper respiratory tract infection in the last 1 month which have not resolved.
2. Lower respiratory tract infection or pneumonia in the last 1 month.
3. Subjects with a positive covid-19 test within 2 weeks of screening
4. Subjects with seasonal allergic rhinitis that affects their asthma control
5. Current smoker or ex-smoker with  $\geq 20$  pack year smoking history and abstinence of  $\leq 6$  months
6. Symptoms of uncontrolled asthma at screening defined as: an exacerbation in the previous month requiring oral prednisone or antibiotics.
7. Use of regular maintenance oral corticosteroids or long-acting muscarinic antagonist within 4 weeks prior to enrolment into the study.
8. A previous asthma exacerbation requiring Intensive Care Unit admission.
9. Significant other primary pulmonary disorders in particular; pulmonary embolism, pulmonary hypertension, interstitial lung disease, lung cancer, cystic fibrosis, emphysema or bronchiectasis.

10. Any history or symptoms of uncontrolled cardiovascular disease, particularly coronary artery disease, uncontrolled arrhythmias, uncontrolled hypertension, or uncontrolled congestive heart failure.
11. Any history or symptoms of significant neurologic disease, including transient ischemic attack, stroke, seizure disorder, or behavioral disturbances
12. Uncontrolled diabetes
13. End stage kidney or liver disease
14. Clinically significant abnormalities in laboratory test results during the screening period (including complete blood count, coagulation, electrolytes, liver function tests) unless deemed not significant by the investigator.
15. Any history or symptoms of clinically significant autoimmune disease
16. History of anaphylaxis to any biologic therapy or vaccine
17. History of Guillain-Barre Syndrome
18. A helminth parasitic infection diagnosed within 24 weeks prior to the date of informed consent is obtained that has not been treated with or has failed to respond to standard of care therapy.
19. Positive hepatitis B surface antigen, or hepatitis C virus antibody serology, or a positive medical history for hepatitis B or C. Subjects with a history of hepatitis B vaccination without history of hepatitis B can enroll.
20. A history of immunodeficiency disorders including a positive human immunodeficiency virus test (HIV)
21. Pregnancy or breast-feeding.
22. Women of childbearing potential (WOCBP) must not be actively seeking pregnancy, and must use an effective form of birth control (confirmed by the Investigator). Effective forms of birth control include: true sexual abstinence, a vasectomized sexual partner, Implanon, female sterilization by tubal occlusion, any effective IUD intrauterine device/IUS levonorgestrel Intrauterine system, Depo-Provera™ injections, oral contraceptive, and Evra Patch™ or Nuvaring™. WOCBP must agree to use an effective method of birth control, as defined above, from enrolment, throughout the study duration and within the 8 treatment weeks. They must demonstrate a negative serum pregnancy test at screening and demonstrate a negative urine pregnancy test immediately before

each dose of study drug or placebo. Women not of childbearing potential are defined as women who are either permanently sterilized (hysterectomy, bilateral oophorectomy, or bilateral salpingectomy), or who are postmenopausal. Women will be considered postmenopausal if they have been amenorrheic for 12 months prior to the planned date of randomization without an alternative medical cause. The following age-specific requirements apply:

- i. Women <50 years old would be considered postmenopausal if they have been amenorrheic for 12 months or more following cessation of exogenous hormonal treatment and follicle stimulating hormone (FSH) levels in the postmenopausal range.
- ii. Women ≥50 years old would be considered postmenopausal if they have been amenorrheic for 12 months or more following cessation of all exogenous hormonal treatment.

23. Male patients not using an acceptable method of contraception. All male patients who are sexually active must agree to use an acceptable method of contraception (condom with or without spermicide, vasectomy) from the first dose of study drug until their last dose.

24. Use of angiotensin-converting-enzyme inhibitors

25. Use of immunosuppressive medication (including but not limited to: methotrexate, cyclosporine, azathioprine, intramuscular long-acting depot corticosteroid, oral corticosteroid, or any experimental anti-inflammatory therapy) within 3 months prior to the date informed consent is obtained

26. Use of any other biological within 4 months or 5 half-lives prior to randomization, whichever is longer.

27. Any centrally acting medication within the last 2 weeks which in the view of the investigator could influence the coughing\*

28. History of psychiatric illness, drug or alcohol abuse which may interfere in the participation of the trial.

*\*Any participant who is taking amitriptyline, dextromethorphan, pregabalin, gabapentin or opioids will not be eligible to take part in this study unless they are willing and medically able to*

*withdraw from such medication for the duration of the study. The reason for this is that centrally acting medications may influence coughing rates.*

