*iv) The Cough Severity Visual Analogue Scale (0-100mm)* is a single item that assesses a patient's severity of cough over a recall period of 1 week using a 0 to 100mm horizontal visual analogue scale (VAS). Participants will rate their severity of cough on the scale which has a minimum value of 0 equalling "no cough" and a maximum value of 100 equalling "worst cough". A higher score indicates greater cough severity.

**Table 1.** Visit and procedure schedule.

Visit	1	2	3	4	5	6	7	8	9
Study Day	1	$13 \pm 7^*$	$14 \pm 3^{\dagger}$	$42 \pm 3^{\dagger}$	$70 \pm 3^{\dagger}$	$71 \pm 3^{\dagger}$	$99 \pm 3^{\dagger}$	$113 \pm 7^{\dagger}$	$114 \pm 3^{\dagger}$
Post-Randomization	-14	-1	0	28	56	57	84	98	99
Week	-2		0	4	8		12	14	
Procedure									
Ontario Covid-19 Assessment Tool	X	X	X	X	X	X	X	X	X
Informed Consent	X								
Medical History	X								
Adverse Events		X	X	X	X	X	X	X	X
Prior and Con Meds		X	X	X	X	X	X	X	X
Examination	X								
Vital Signs	X	X	X	X	X	X	X	X	X

Urine B-HCG ¥	X		X	X	X		X		
Spirometry	X		X			X			X
Cough Monitoring		X			X			X	
Methacholine PC 20	X								X
Induced Sputum	X #		X			X			X
Blood Sampling	X		X	X		X	X		X
LCQ	X		X	X		X	X		X
mBorg Scale	X		X	X		X	X		X
Cough Severity VAS	X		X	X		X	X		X
Mepolizumab/Placebo			X	X	X		X		

\* May be shortened to 7 days or extended to 21 days depending on availability of sputum cell counting to confirm eligibility of sputum eosinophilia >2%.

†Flexibility provided to allow visits cough monitoring on Friday and subsequent visit on Monday.

¥ Urine pregnancy test will be done for women of childbearing potential (WOCBP) prior to administration of IP.

#Sputum induction at visit 1 could be repeated after 24-48 hours if insufficient sample at visit 1.

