## 6. Investigational Product

### 6.1. Formulation

All investigational products will be manufactured in accordance with Good Manufacturing Practice (GMP). Mepolizumab and placebo will be supplied by GSK in 1ml pre-filled syringes (Table 2). Mepolizumab 100mg or a normal (0.9%) saline placebo subcutaneous injection will be administered at the study centre on days 0, 28, 56 and 84 during the 12 week treatment period. The placebo will have an appearance identical to that of the study drug. Those administering treatment, any study staff involved in subject evaluations, and the subjects will remain blind to treatment assignment for the duration of the study.

**Table 2.** Intervention, dose, form, strength, and manufacturer per intervention.

Intervention	Dose	Form	Strength	Manufacturer
Mepolizumab	100mg	pre-filled (1ml) solution in syringe	100 mg/ml	GSK
Placebo - 0.9% normal saline	N/A	pre-filled (1ml) solution in syringe	N/A	GSK

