### 6.2. Dosage Regimen

Patients will be randomized in 1:1 to receive mepolizumab 100mg monthly (4 doses) or matched placebo (4 doses) over 12 weeks.

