#### *8.1.2. Serious Adverse Events*

Any adverse event, adverse reaction or unexpected adverse reaction, respectively, that:

- Results in death
- Is life threatening
- Requires admission to hospital or prolongation of hospitalisation
- Results in persistent or significant disability/incapacity

- Is a congenital anomaly or birth defect
- Is otherwise medically significant

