### 8.2.1. GSK Reporting Procedures

All safety reports and associated information, including the investigator's causality assessment, as presented in Table 3 that occur during the study in subjects exposed to the IP will be sent by email to GSK's Case Management Group (Americas), marked for the attention of the Case Administrator: [contact] or [contact] and to [name] : [contact] or [contact]. All safety reports will be submitted within 1 working day of the Principal Investigator becoming aware of the event.

Any SAEs reported by study subjects during the study which the investigator considers there to be a reasonable possibility of a causal association to any other known GSK product taken concurrently with the IP will be forwarded to GSK within 24 hours of the investigator becoming aware of the event, regardless of investigator/sponsor expectedness assessments.

Further detailed information about safety reports will be submitted to GSK within 24 hours of follow-up information becoming available.

Events exempt from reporting to GSK include any unblinded reports for subjects exposed only to placebo during the study.

The safety reports and information that are subject to the presented GSK reporting provisions are those that occur following the 1st dose of the IP through to 28 days or 5 terminal phase half-lives (whichever is longer) following discontinuation of the IP.

**Table 3.** GSK reporting safety events and information procedure

Safety Data	Format	Time Line
All SAEs that are unblinded during the course of the study, for which the investigator considers there to be a reasonable possibility of causal association with the GSK IP (as specified by the protocol), regardless of Investigator/designee/Sponsor expectedness assessments against GSK IP	Copies of Case Report Form pages	Within 24 hours of Sponsor first unblinding the event

All SAEs that remain blinded on the Sponsor database during the course of the study, where the investigator considers there to be a reasonable possibility of causal association with the GSK IP (as specified by the protocol), regardless of Investigator/designee/Sponsor expectedness assessments against GSK IP.	Copies of regulatory reports (e.g., CIOMS 1 or MedWatch)	Retrospectively within five working days of the Sponsor unblinding the study database

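### Exclusion 22 cites 8 treatment weeks for a 12-week regimen and sets no post-dose contraception period, so cover for women ends at Visit 9, nominally 15 days after dose 4

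*Combined protocol and SAP*

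**What the plan says.** Section 5.7, exclusion 22, sets the birth-control period for women of childbearing potential as "from enrolment, throughout the study duration and within the 8 treatment weeks". It states no interval after the last dose.

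The treatment schedule is consistent everywhere else. Section 6.1 places the injections "on days 0, 28, 56 and 84 during the 12 week treatment period", and sections 5.1 and 6.2 also give four doses over 12 weeks. Section 5.2 makes participation up to 2 weeks of screening plus a "14-week intervention period", with no follow-up phase. Section 5.10.2 names Visit 9 as the final visit. Section 5.1 says the effect on cough "will be tested at week 14, 2 weeks following the last dose of mepolizumab/placebo".

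Two safety provisions bear on the period after dose 4. Section 8.2.1 applies the funder's safety-reporting terms from the first dose "through to 28 days or 5 terminal phase half-lives (whichever is longer) following discontinuation of the IP". Section 8.1.2 includes among serious adverse events one that "Is a congenital anomaly or birth defect".

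Table 1 schedules urine pregnancy tests at Visits 1, 3, 4, 5 and 7, and none at Visits 8 or 9.

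**The concern.** The 8-week figure matches no treatment period in the protocol. Once it is set aside, the only end point left in the clause is the end of the study, which comes about halfway through the dosing interval that follows dose 4.

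The urine tests before each injection guard against dosing a woman who is already pregnant. They do nothing about conception after dose 4. A woman who follows the criterion as written may stop contraception at Visit 9, the day after the primary cough recording starts. That recording is timed to capture drug effect. If she then conceives, no scheduled study procedure would detect it, although the protocol counts birth defects within its safety scope. No reason is given for ending cover at that point.

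**Working it through.** All days are from the post-randomization row of Table 1 (dose 1 = day 0) unless marked as study days.

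**Inputs.** Doses on days 0, 28, 56 and 84 (sections 5.1 and 6.1; Table 1). Visit 8, the primary recording, on day 98 (section 9.2.2; Table 1). Visit 9 on day 99 (Table 1). Post-dose reporting window: the longer of 28 days and five half-lives (section 8.2.1). Half-life: not in the documents.

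**1. The 8-week figure.** First to last dose: (84 − 0) / 7 = 12 weeks. Eight weeks from dose 1 is 8 × 7 = day 56, the day of dose 3, which is 84 − 56 = 28 days before dose 4. The figure is therefore not reproduced from the schedule. It does not shorten cover, because the same clause also runs through the study duration, beyond day 56.

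**2. Where cover ends as written.** Visit 9 minus dose 4: 99 − 84 = 15 days. The study-day row agrees: 114 − 99 = 15. Visit 9 is 99 − 98 = 1 day after the primary recording starts. Counting only to the end of the 14-week period in section 5.2 gives 14 × 7 − 84 = 14 days.

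**3. Against the plan's own intervals.** Shortfall from one dosing interval: 28 − 15 = 13 days, or 13 / 28 = 46% of the interval. The 28-day minimum in section 8.2.1 ends on day 84 + 28 = 112, and 112 − 99 = 13 days after Visit 9.

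**4. Five half-lives.** These outlast Visit 9 if the half-life exceeds 15 / 5 = 3.0 days, 28 days if it exceeds 28 / 5 = 5.6 days, and 8 weeks if it exceeds 56 / 5 = 11.2 days. Over an assumed range:

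| Assumed half-life (days) | Five half-lives after dose 4 (days) | Days beyond Visit 9 |
|---|---|---|
| 10 | 50 | 50 − 15 = 35 |
| 15 | 75 | 75 − 15 = 60 |
| 20 | 100 | 100 − 15 = 85 |

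**5. If 8 weeks after the last dose was meant.** 84 + 56 = day 140, and 140 − 99 = 41 days after Visit 9.

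**6. Monitoring after dose 4.** Pregnancy tests scheduled after dose 4: 0. Visits after Visit 9: 0.

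**The case against.** The best defence is that the clause works. It covers the whole study, all four doses fall inside that period, and the 8-week phrase is a redundant slip. That much stands. A reader might infer that dose 4 is left uncovered, or that the clause cannot be applied at all; neither follows, because the study duration gives it a usable end point.

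A reader might also infer that staff would give women instructions differing by 41 days. That requires rewording the phrase as 8 weeks after treatment. The text does not say this, and a leftover from another schedule, which would add no cover, fits equally well. The 41 days measures one possible intention and is not evidence of conflicting advice.

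Nor do the documents show that 15 days is unsafe. They give no half-life, and section 8.3 lists no reproductive risk. The dosing interval, the timing of the cough recording and the reporting window are all proxies, and section 8.2.1 is a reporting rule that does not extend participation. They show only that the clause is out of line with the plan's other post-dose intervals, without explanation.

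Table 1's visit windows might suggest that Visit 9 always falls within 28 days of dose 4. It need not. Visit 7 three days early (study day 96), Visit 8 seven days late (study day 120) and the allowance described as "Flexibility provided to allow visits cough monitoring on Friday and subsequent visit on Monday" (study day 123) give 123 − 96 = 27 days. The repeat recording allowed at Visit 9, up to 48 hours later, makes 29. Only the nominal 15 days is relied on here.

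The context limits the scale. Section 1.2 says prevalence peaks in the 50s and 60s, so few of about 30 randomized participants may be affected. Exclusion 22 bars women actively seeking pregnancy, and several permitted methods, such as an IUD or tubal occlusion, would not lapse at Visit 9. The consent pages were not available and may state a period, though that would not correct the criterion. No endpoint or analysis is touched.

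**Conclusion.** The point holds as a safety-wording defect that should be corrected. The 8-week figure contradicts the 12-week, four-dose regimen. The requirement as written ends nominally 15 days after dose 4, which is 13 days short both of one dosing interval and of the 28-day minimum in section 8.2.1, with no later pregnancy test or visit.

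This rests on reading study duration as ending at Visit 9, which sections 5.2 and 5.10.2 support, and on using the reporting window only as a benchmark. The size of any gap against five half-lives depends on a half-life the documents do not give. What was meant by the 8-week phrase cannot be settled from the text. Confidence is medium.

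**What to change.** Delete the reference to 8 treatment weeks. Require contraception from enrolment, throughout the study, and for a fixed number of days after the last dose. The sponsor should set that number as the longer of 28 days and five half-lives, or 8 weeks if that was the intention and is longer still. A fixed number spares site staff from working out the half-life. Simply changing 8 to 12 is not enough: it would leave the end of cover at Visit 9 and could erase an intended post-treatment period.

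The cost is an amendment to exclusion 22 and to any matching consent text. Women of childbearing potential, whose number the plan does not give, would use contraception beyond Visit 9 for at least 13 days more. If 8 weeks governs, it is 41 days more. If five half-lives governs, it is about 35 to 85 days more at assumed half-lives of 10 to 20 days. No visit, assay or analysis changes.

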## **5.8. Recruitment Process**

Participants will be recruited by clinicians from clinics at either of the following sites:

- a) McMaster University Medical Centre, Department of Respiratory Medicine, [name]
- b) Firestone Institute for Respiratory Health, St Joseph’s Healthcare, [name]

All study visits will take place at McMaster University, Cardio-Respiratory Research Laboratory, Faculty of Health Sciences, [name].

## **5.9. Informed Consent**

Patients recruited to participate in the study will meet with study staff and receive the participant information sheet. Patients will be given the opportunity to ask study staff questions about the study. Patients who express an interest in participating in the study will provide their fully informed written and verbal consent to be enrolled in the study. Informed consent will be obtained at the screening visit before any study procedures are conducted. Patients will also be informed that mepolizumab is currently licensed in Canada for treatment of patients with severe eosinophilic asthma only. If a patient’s chronic cough improves whilst on the active treatment, mepolizumab is currently not licensed from the treatment of chronic cough.

### *5.9.1. Associated Risks and Benefits to Subjects*

#### *Benefits*

Subjects will benefit from regular assessment of lung physiology, blood and airway inflammation and cough frequency. Along with helping to advance our understanding of the mechanisms causing chronic cough and to develop potentially improved treatments, the subject will benefit from being reviewed by a chest specialist.

#### *Risks*

The common risk of treatment with mepolizumab from placebo-controlled studies is local injection site reaction. In 2 placebo-controlled studies the incidence of local injection site reactions with mepolizumab 100 mg subcutaneous and placebo was 8% and 3%, respectively. These events were all non-serious, mild to moderate in intensity and the majority resolved within a few days. Local injection site reactions occurred mainly at the start of treatment and within the first 3 injections with fewer reports on subsequent injections. The most common manifestations reported with these events included pain, erythema, swelling, itching, and burning sensation. A full list of adverse events are tabulated in section 8.3 below.

It is possible that subjects may develop an increase in their asthma symptoms during the with-holding of asthma medication before the methacholine challenge on visit 1. Should this happen, patients will be advised to re-start their medication and inform the principle investigator. There will be an on-call study physician who is contactable outside of working hours should advice be needed.

The main risk of performing a methacholine challenge is that of developing asthma symptoms, due to the fall in FEV1. The American Thoracic Society (ATS) has published a detailed guideline for performing methacholine challenge, which we have adopted for our local standard operating procedure (SOP) to maintain international standards (31).

Sputum induction using hypertonic saline carried a small risk of a fall in lung function along with a salty unpleasant taste at the back of the mouth.

Precautions will be taken for patient safety such as the availability of monitoring equipment (spirometer, pulse oximeter, blood pressure monitor) and short acting bronchodilators (salbutamol and ipratropium via inhaler/nebuliser), oxygen, and resuscitation equipment.

